## C. APPROACH

**C1. Overview.** *We propose a single-center, randomized and controlled but not blinded clinical trial to assess what variables predict further response to CPAP after AT (Figure 1). Potential inclusion of any child, regardless of post-operative polysomnographic results at 4 months, will allow the full spectrum of polysomnographic results to be tested as predictors of neurobehavioral response to CPAP. Standard cut-offs used to define clinically significant SDB remain untested in the post-AT setting, but will be applied first to test hypotheses 1a, 1b, and 2a. Other cut-offs and continuous measures that have been proposed by our group and others also will be tested in key exploratory analyses that could prove highly informative. The protocol will allow for example assessment of the possibility that clinical symptoms as detected on a questionnaire, but too insensitive to register on polysomnography, still deserve treatment. Every child who participates in this protocol will stand a chance to benefit. Two-thirds will receive CPAP; no standard care will be denied; and at the end of the study, summaries of sleep and neurobehavioral findings will be made available to all families, along with guidance on how to obtain follow-up clinical care for any remaining concerns.*

**C2. Subjects.** Recruitment will be directed by co-investigator [name], a University of Michigan pediatric otolaryngologist, with the assistance of 4 additional otolaryngologists in the Division of Pediatric

Otolaryngology, and 4 at St. Joseph Mercy Hospital in Ann Arbor. Both groups of surgeons have energetically supported recruitment for the PI's sleep research on children undergoing AT for the past 10 years. Surgeons or clinic office personnel will ask each parent or guardian of a child scheduled to undergo full AT for suspected SDB whether he or she would be willing to hear about the research. If so, a brief signed consent will be faxed to the investigators, who will initiate discussion by phone and then invite the family to the sleep laboratory to

[figure not shown]

Figure 1

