Approximately ten months after AT (six months after randomization), sleep studies (on steady PAP for the CPAP subjects, without PAP for controls) and neurobehavioral assessments will all be repeated. The sleep study is required to precede a valid Multiple Sleep Latency Test; will allow confirmation in CPAP subjects that any SDB is well controlled; and will allow reassessment for residual SDB in the control group. The 6-month interval is selected to ensure adequate time for PAP habituation, neurobehavioral response to consistent use of PAP, and acceptably low risk of test-retest learning effects on cognitive measures. The outcome measures have been used by the investigators in two NIH-funded R01s (HD038461 and HL080941) over the past 10 years and all derive from well-validated, widely accepted instruments. The explanatory polysomnographic measures are all consistent with American Academy of Sleep Medicine 2007 standards. Esophageal pressure monitoring, with which this laboratory has extensive clinical, research, and published experience, will be used to provide a gold-standard assessment of respiratory effort. In addition, at least 3 highly innovative, most promising, and particularly sensitive computerized measures, all pioneered previously in children by the investigators, will be available to complement standard analyses. These include respiratory cycle-related EEG changes (RCREC) thought to reflect subtle but numerous and consequential inspiratory microarousals; an analysis of sleep dynamics, which focus on continuity of sleep and specific sleep stage bouts rather than traditional totals of time spent in each stage; and quantitative analysis of esophageal pressure swings during each respiratory cycle through the night. Based on the investigators' preliminary data (see below and section C9.5), these automated measures may well improve the ability of pediatric polysomnography to distinguish children with and without clinically significant SDB and potential to benefit from CPAP.

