One week prior to each sleep study, an investigator will call the family to confirm the appointment, verify absence of unexpected illness, and encourage completion of a one-week sleep log. Nocturnal sleep studies will be performed by registered, child-experienced sleep technologists in the 10-bed Michael S. Aldrich Sleep Disorders Laboratory, where 4 spacious rooms specifically designed to accommodate young children, and parents in a separate bed, are available also for research use. *Weight and height will be measured at the laboratory.* The next day, a Multiple Sleep Latency Test will be administered. Between naps, a trained technician will administer neuropsychological tests. All children will be tested after a night in the same environment, equivalent opportunities for good sleep, and measured total sleep times. During each child's testing, a parent will complete behavioral rating scales, the Pediatric Sleep Questionnaire (described above), and a standard measure of socioeconomic status. After the sleep studies at 4 months post-AT, submission of electronic adherence data (CPAP group) or other follow-up information (control group) at 7 months, and final assessments at 10 months, each child will receive a \$30 gift certificate. After evaluations at 4 months and 10 months post-AT, each parent will receive \$250 for their time spent on this research. Parents will also be compensated for timely, monthly follow-up contacts (\$5 for each contact completed within 5

business days of the target follow-up call date), which are important in assessing possible safety concerns on study.

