An unmasked, board-certified sleep specialist will interpret each sleep study, not to provide study variables but rather to inform families and their physicians. Study results generally will not be communicated until after the participant has finished the entire protocol, when sleep and psychological test results are fully scored. However, an investigator will promptly communicate any finding that could have medically urgent significance for the patient, such as an unsuspected arrhythmia, paroxysmal EEG spikes, or severe residual SDB.

Nocturnal polysomnograms and Multiple Sleep Latency Tests will be scored by a single chief technologist ([name], RPSGT, REEGT) masked to subject identity. This technologist has meticulously scored about 1,000 pediatric sleep research studies in the past 10 years. Borderline polysomnographic features will be arbitrated between the technician and the PI. Scoring will be performed in batches: pre- and post-PAP studies of 5 subjects will be randomly ordered and presented for scoring. This procedure, used for two past R01s, assures that any subtle changes in scoring tendencies over time do not confound pre- vs. post-PAP comparisons. Scoring for sleep stages, respiratory events, periodic leg movements, and arousals will follow standard criteria for children. Double-scoring of arousals and respiratory events, in 20% of the records, will be performed to generate a Kappa statistic for intra-rater reliability. Inter-rater reliability will also be determined by having another experienced polysomnographic technologist score these same records.

For Multiple Sleep Latency Tests, the sleep latency of each nap will be scored as the time between lights out and the first epoch of stage 1 sleep. The mean sleep latency across naps is the most well-validated and commonly used objective measure of daytime sleepiness in both adults and children. Childhood sleepiness as a continuous variable for research purposes can be detected in SDB patients as young as 3 years old by questionnaires and by Multiple Sleep Latency Tests.

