**Cognitive Assessments.** Tests will be administered by an experienced, neuropsychologist-supervised psychometrist who is well trained to maintain children's motivation and monitor the need for rest breaks or changes in conditions. Each child also will receive a brief introduction to face-to-face testing using CogState (described below) during the time just following consent signing. As many children will not have had the experience of being tested before, this introduction will reduce apprehension and familiarize each child with the types of materials to be tested. The total testing time for post-AT sessions will be approximately 2 hours, spread between nap studies. This is less time than routine clinical evaluations (usually 4-8 hours). All specific test sessions will occur at the same time of day, without variance between subjects or test and retest visits.

The Attention/Executive Functions domain score of the NEPSY-II and the computerized continuous performance test, Integrated Variables of Attention, will comprehensively cover short term and sustained attention, vigilance, impulsivity, and executive ability. Overall intelligence and academic achievement will be assessed briefly using the two Stanford-Binet, 5th Edition (SB5) "routing tests", Matrices and Vocabulary and selected Woodcock Johnson-III subtests (Letter Word Identification, Reading Fluency, Calculation, and Applied Problems). The Selective Reminding Test is sensitive to children's memory, specifically verbal encoding and retrieval. Speed and control of fine motor ability will be measured with the Purdue Pegboard. Finally, the brief computerized CogState battery will provide valid indices of processing speed, working memory, executive functioning, and memory in a combined measure that remains stable over time, incorporates simple response requirements and self-contained training modules, and has proven inherently interesting and motivating, and sensitive to subtle cognitive change in children. This test also includes the Groton Maze Test, a brief, computerized measure of psychomotor speed and visuospatial problem solving.

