##### **(b) Secondary Outcome Measures:**

1. Neurocognitive change after AT (hypothesis 2c CPAP vs controls intent to treat)

Change in **NIH Toolbox Total Composite Score Age Adjusted** following 6 months of CPAP vs. no CPAP use by children after AT

2. Change in subjective sleepiness after AT (hypothesis 2c CPAP vs controls intent to treat)

Change in **Epworth Sleepiness Scale score** following 6 months of CPAP vs. no CPAP use by children after AT

3. Change in objective sleepiness after AT (hypothesis 2c CPAP vs controls intent to treat)

Change in **MSLT** following 6 months of CPAP vs. no CPAP use by children after AT

4. Change in quality of life (hypothesis 2c CPAP vs controls intent to treat)

Change in **PedsQL** following 6 months of CPAP vs. no CPAP use by children after AT

5. For CPAP subjects, neurobehavioral outcomes will improve more from baseline to follow up among those who have adhered to CPAP than those who are non-adherent (hypothesis 2b)

Change in **behavioral index** from SV2 to SV4 in adherent vs non-adherent CPAP users

6. For CPAP subjects, neurobehavioral outcomes will improve more from baseline to follow up among those who have adhered to CPAP than those who are non-adherent (hypothesis 2b)

Change in **NIH Toolbox Total Composite Score Age Adjusted** from SV2 to SV4 in adherent vs non-adhere

7. For CPAP subjects, neurobehavioral outcomes will improve more from baseline to follow up among those who have adhered to CPAP than those who are non-adherent (hypothesis 2b)

Change in **ESS** from SV2 to SV4 in adherent vs non-adherent CPAP users

8. For CPAP subjects, neurobehavioral outcomes will improve more from baseline to follow up among those who have adhered to CPAP than those who are non-adherent (hypothesis 2b)

Change in **MSLT** from SV2 to SV4 in adherent vs non-adherent CPAP users

9. For CPAP subjects, neurobehavioral outcomes will improve more from baseline to follow up among those who have adhered to CPAP than those who are non-adherent (hypothesis 2b)

Change in **PedsQL** from SV2 to SV4 in adherent vs non-adherent CPAP users

10. Among adherent CPAP users residual SRBD score at SV2 will predict greater improvement at SV4 for behavior (hypothesis 2a)

Change in **behavioral index** from SV2 to SV4 in CPAP adherent subjects will be associated with SRBD score at SV2

11. Among adherent CPAP users residual SRBD score at SV2 will predict greater improvement at SV4 for cognition (hypothesis 2a)

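### No masking is planned for the psychometrist who gives the study visit 4 cognitive tests, which leaves the cognitive secondary outcome at avoidable risk of assessor bias

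*Combined protocol and SAP*

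**What the plan says.** C1 describes a "single-center, randomized and controlled but not blinded clinical trial". Masking is then mentioned only in C4. There, the technologist who scores the polysomnograms and MSLTs is "masked to subject identity", and the specialist who reads the sleep studies for families is described as unmasked.

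On cognition, C5 (Cognitive Assessments) states: "Tests will be administered by an experienced, neuropsychologist-supervised psychometrist who is well trained to maintain" the children's motivation. The same person watches for the need for breaks or altered conditions, and section 6.2.b repeats that breaks are given as needed. Whether this person knows the child's arm is not said.

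On timing, C3 states that about ten months after surgery "sleep studies (on steady PAP for the CPAP subjects, without PAP for controls) and neurobehavioral assessments will all be repeated". The tests follow on the day after the laboratory night: "Between naps, a trained technician will administer neuropsychological tests". C3 also says: "All children will be tested after a night in the same environment, equivalent opportunities for good sleep, and measured total sleep times".

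On the outcome, C7(b) item 1 makes change in the "NIH Toolbox Total Composite Score Age Adjusted" the first secondary outcome for the intent-to-treat comparison of CPAP with control (H2c). The same score returns in items 6, 11 and 16 for H2b and H2a.

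**The concern.** Families in a trial of CPAP against no CPAP cannot be masked, but a cognitive tester can be. The plan deals with masking for two sleep-laboratory roles and leaves out the one person whose conduct during a test session could affect a child's score. Encouragement, break-giving and adjustment of conditions are left to that person's judgement, and judgement of this kind can drift with knowledge of the arm.

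At stake is how a cognitive result can be read. The primary Behavioral Index is rated by parents who know the arm, and C5 itself acknowledges possible parental bias. A performance test is useful next to such a rating because it does not depend on the parent. If the tester may know the arm, a difference in favour of CPAP invites the reply that the tester treated the groups differently, and the trial would have no data with which to answer it. For H2b and H2a, knowledge of a child's adherence raises the same question within the CPAP group.

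**Working it through.** The point rests on the text, so the passages are set side by side first. I take the psychometrist of C5, the technician of C3 and the neuropsychology technician of 6.2.b to be the same role.

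1. **Is masking of the tester planned?** C1 gives a general statement that the trial is not blinded. C4 makes one exception for an outcome assessor, the sleep scorer. C5 makes none. No masking of the tester is planned in the text.
2. **Could the tester learn the arm?** At SV4 the CPAP group has just slept in the laboratory on PAP and the controls have not (C3). Testing is in the same setting the next day. C6 adds a seven-item survey of children and parents, in both arms, about their experience or health during the study, given again at the endpoint visit. Nothing says that it comes after testing or is handled by someone else. No concealment step is described anywhere.
3. **Does the tester have discretion?** Yes, over motivation, breaks and conditions (C5; 6.2.b).
4. **How far does the outcome depend on the tester?** C5 identifies the continuous performance test and CogState, with its maze test, as computerized. It does not so describe NEPSY-II, Stanford-Binet, Woodcock-Johnson, Selective Reminding or the Purdue Pegboard. The named outcome is the NIH Toolbox composite, which C5 introduces as a possible substitute. The documents do not say how much of it depends on the examiner.
5. **What is exposed?** 80 + 40 = 120 planned SV4 cognitive assessments, and items 1, 6, 11 and 16, which are 4 of the 19 listed secondary outcomes.

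**Sensitivity to a small bias (illustration only).** C9 gives no effect size or power for cognition. Its H2c figure is for the Behavioral Index: 80 against 40, effect size 0.55, 80% power. I use it only to confirm the standard error, taking two-sided alpha 0.05 as an assumption, because C9 states .05 for H1a without sidedness.

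- SE of the arm difference in SD units = √(1/80 + 1/40) = 0.1936.
- Power = Φ(0.55/0.1936 − 1.960) = Φ(0.880) = 81.1%. The t-test version gives 80.4%. C9's 80% is reproduced.

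Suppose there is no true effect and the tester adds a between-arm bias b, in SD units. The chance of a significant result is then Φ(b/SE − 1.960) + Φ(−b/SE − 1.960).

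| Assumed b (SD) | Type I error |
|---|---|
| 0 | 5.0% |
| 0.05 | 5.8% |
| 0.10 | 8.1% |
| 0.20 | 17.8% |
| 0.30 | 34.1% |

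No value of b comes from the documents. The table shows only what a given bias would do at this sample size; it does not estimate the bias.

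**The case against.** The strongest reply is that the documents are silent about this person and that silence is not a plan to unmask. C1's label is general, the same protocol does mask one assessor, and operational detail is deferred to manuals that are not part of the documents. This stands in part. A reader might infer that the tester is known to be unmasked and that the cognitive result carries bias; the text supports neither. It supports the statement that no masking is planned and that a risk follows.

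Other replies also have weight:

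- **The PAP night.** Sleeping on PAP before SV4 is the planned treatment condition. It is a route by which the tester may learn the arm and is not in itself a bias. Nothing says that PAP equipment stays in the test room.
- **Standardisation.** Sessions are at a fixed time of day, after a night in a common environment, under neuropsychologist supervision, and many tests have equated forms. This limits variation in conditions but does not remove discretion over encouragement and breaks.
- **Other sources.** A reader might infer that cognition is the sole evidence free of parent or child report. It is not. C5 provides teacher forms of three behavioural scales, partly to address parental bias (C7 does not list them as outcomes), and the MSLT is scored by a masked technologist.
- **Size.** It is tempting to express an assumed shift as a share of the 0.55 effect size. That figure belongs to the Behavioral Index, which the psychometrist does not administer, so the ratio would mean nothing for cognition.
- **The Toolbox composite.** If most of it is computer-administered, the exposure is smaller. The documents leave this open.

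**Conclusion.** The concern holds as a risk. The plan masks the sleep scorer but plans no masking for the cognitive tester, who has discretion during testing and sees CPAP children the day after a night on PAP. The first-listed secondary outcome is therefore open to an assessor bias that could be reduced at little cost. All 120 planned SV4 cognitive assessments are exposed. The direction and size of any bias cannot be derived from the documents.

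The primary Behavioral Index does not pass through the tester and is unaffected. Sample size and power are unchanged. The change is worth making but is not a condition for the trial's main comparison.

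The conclusion assumes that the operations manual does not already mask the tester. If it does, a sentence in C5 settles the point.

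**What to change.** In C5, state for SV4 that:

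- the tester is not told the arm and has no part in PAP set-up, adherence contacts or the interval visit;
- PAP equipment is out of sight before daytime testing starts;
- parents and children are asked beforehand not to mention PAP to the tester;
- the endpoint experience survey is given after testing or by someone else;
- after testing, the tester records a guess of the arm, and the guesses are reported by arm.

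Amend C1 to say that the trial is open to families, with the cognitive tester and the sleep scorer masked. It would also help to say in C5 which parts of the Toolbox composite the examiner administers.

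The cost is a few lines in the protocol and the manual. The psychometrist, tests and visits stay the same. C6 already gives PAP set-up, adherence support and the interval visit to the equipment provider, nurse, psychologist and other study staff, so the main need is to state that the tester is not among them. The downside is that masking will fail for some children who mention PAP; the recorded guess will show how often.

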#### **C7. Outcome Measures:**

This section defines the outcome measures to be gathered for this trial, classified into primary, secondary and exploratory. Other measures referred to anywhere within the protocol are to be considered baseline, exploratory for cross-analyses or safety related, as appropriate. Study visit 2 (SV2) represents the initial polysomnogram approximately 4 months following AT and study visit 4 (SV4) represents the final polysomnogram approximately 6 months later (equivalent to approximately 10 months after AT).

##### **(a) Primary Outcome Measure:**

1. Neurobehavioral change (hypothesis 2c CPAP vs controls intent to treat)

Change in **behavioral index** following 6 months of CPAP vs. no CPAP use by children after AT

##### **(b) Secondary Outcome Measures:**

1. Neurocognitive change after AT (hypothesis 2c CPAP vs controls intent to treat)

Change in **NIH Toolbox Total Composite Score Age Adjusted** following 6 months of CPAP vs. no CPAP use by children after AT

2. Change in subjective sleepiness after AT (hypothesis 2c CPAP vs controls intent to treat)

Change in **Epworth Sleepiness Scale score** following 6 months of CPAP vs. no CPAP use by children after AT

3. Change in objective sleepiness after AT (hypothesis 2c CPAP vs controls intent to treat)

Change in **MSLT** following 6 months of CPAP vs. no CPAP use by children after AT

4. Change in quality of life (hypothesis 2c CPAP vs controls intent to treat)

Change in **PedsQL** following 6 months of CPAP vs. no CPAP use by children after AT

5. For CPAP subjects, neurobehavioral outcomes will improve more from baseline to follow up among those who have adhered to CPAP than those who are non-adherent (hypothesis 2b)

Change in **behavioral index** from SV2 to SV4 in adherent vs non-adherent CPAP users

6. For CPAP subjects, neurobehavioral outcomes will improve more from baseline to follow up among those who have adhered to CPAP than those who are non-adherent (hypothesis 2b)

Change in **NIH Toolbox Total Composite Score Age Adjusted** from SV2 to SV4 in adherent vs non-adhere

7. For CPAP subjects, neurobehavioral outcomes will improve more from baseline to follow up among those who have adhered to CPAP than those who are non-adherent (hypothesis 2b)

Change in **ESS** from SV2 to SV4 in adherent vs non-adherent CPAP users

8. For CPAP subjects, neurobehavioral outcomes will improve more from baseline to follow up among those who have adhered to CPAP than those who are non-adherent (hypothesis 2b)

Change in **MSLT** from SV2 to SV4 in adherent vs non-adherent CPAP users

9. For CPAP subjects, neurobehavioral outcomes will improve more from baseline to follow up among those who have adhered to CPAP than those who are non-adherent (hypothesis 2b)

Change in **PedsQL** from SV2 to SV4 in adherent vs non-adherent CPAP users

10. Among adherent CPAP users residual SRBD score at SV2 will predict greater improvement at SV4 for behavior (hypothesis 2a)

Change in **behavioral index** from SV2 to SV4 in CPAP adherent subjects will be associated with SRBD score at SV2

11. Among adherent CPAP users residual SRBD score at SV2 will predict greater improvement at SV4 for cognition (hypothesis 2a)

Change in **NIH Toolbox Total Composite Score Age Adjusted** from SV2 to SV4 in CPAP adherent subjects

will be associated with SRBD score at SV2

12. Among adherent CPAP users residual SRDB score at SV2 will predict greater improvement at SV4 for subjective sleepiness (hypothesis 2a)

Change in **ESS** from SV2 to SV4 in CPAP adherent subjects will be associated with SRBD score at SV2

13. Among adherent CPAP users residual SRDB score at SV2 will predict greater improvement at SV4 for objective sleepiness (hypothesis 2a)

Change in **MSLT** from SV2 to SV4 in CPAP adherent subjects will be associated with SRBD score at SV2

14. Among adherent CPAP users residual SRDB score at SV2 will predict greater improvement at SV4 for quality of life (hypothesis 2a)

Change in **PedsQL** from SV2 to SV4 in CPAP adherent subjects will be associated with SRBD score at SV2

15. Among adherent CPAP users AHI at SV2 will predict greater improvement at SV4 for behavior (hypothesis 2a)

Change in **behavioral index** from SV2 to SV4 in CPAP adherent subjects will be associated with AHI at SV2

16. Among adherent CPAP users AHI at SV2 will predict greater improvement at SV4 for cognition (hypothesis 2a)

Change in **NIH Toolbox Total Composite Score Age Adjusted** from SV2 to SV4 in CPAP adherent subjects will be associated with AHI at SV2

17. Among adherent CPAP users AHI at SV2 will predict greater improvement at SV4 for subjective sleepiness (hypothesis 2a)

Change in **ESS** from SV2 to SV4 in CPAP adherent subjects will be associated with AHI at SV2

18. Among adherent CPAP users AHI at SV2 will predict greater improvement at SV4 for sleepiness (hypothesis 2a)

Change in **MSLT** from SV2 to SV4 in CPAP adherent subjects will be associated with AHI at SV2

19. Among adherent CPAP users AHI at SV2 will predict greater improvement at SV4 for quality of life (hypothesis 2a)

Change in **PedsQL** from SV2 to SV4 in CPAP adherent subjects will be associated with AHI at SV2

